9.4 Statistical Analyses

The SAP will be finalised prior to database lock for the interim analysis and will include a more technical and detailed description of the statistical analyses described in this section. This section is a summary of the planned statistical analyses of the most important endpoints including primary and key secondary endpoints.

9.4.1 General Considerations

All results will be presented by treatment group and overall, with descriptive statistics appropriate to the nature of the variables.

Demographic and baseline characteristics as well as prior and concomitant medication will be presented. For continuous variables, the number of non-missing observations, mean, SD, median, first and third quartiles, minimum, and maximum will be presented. For categorical variables: counts (n) and percentages (%) (where specified) will be presented. These

summaries will be provided by timepoint of assessment as appropriate.

When change from baseline will be described, the baseline value will be, in general, the last non-missing value prior to administration of the first dose of each treatment period. Further details will be described in the SAP.

The SAS[®] version 9.4 or later will be used for the data analysis.

In general, there will be no imputation of missing data for the safety analyses. Additional details will be provided in the SAP.

Deviations from the protocol will be assessed as "important" or "not-important". Important deviations from the protocol may lead to the exclusion of participants from any of the study analysis sets. Deviations will be defined before database hard lock. Important deviations will include the following:

- Violation of inclusion and/or exclusion criteria
- Administration of prohibited concomitant medications that are expected to influence the measurement of the primary endpoint.

All protocol deviations will be discussed at the data review meeting prior to database hard lock in order to define the analysis sets for the study. All the important protocol deviations will be listed by participants. Further details will be described in the SAP.

9.4.2 Efficacy

The analysis of all efficacy variables will be performed on the FAS. In addition, the primary efficacy endpoint will also be analysed using the PPS, as a sensitivity analysis.

9.4.2.1 Primary Endpoint

The primary efficacy endpoint for this study is the percent change from baseline in UACR at 12 weeks.

Baseline for UACR will be defined as the geometric mean of 3 UACR values derived from samples collected at consecutive days prior to the first dose of study treatment.

As UACR is assumed to follow a log-normal distribution, it will be log transformed for statistical analysis purposes. The mean log percent changes in UACR at 12 weeks for each of the 3 doses of AZD9977 combined with dapagliflozin 10 mg and dapagliflozin 10 mg alone will be estimated in a mixed model for repeated measures (Visits 7, 8, 9, and 10). The values will be back-transformed onto the original scale to give the geometric mean relative percent change from baseline at 12 weeks.

Patients randomised according to CSP versions 1.0 to 5.0 (before dropping placebo and AZD9977 150 mg monotherapy arms) will be considered as part of Cohort 1, while patients randomised subsequently will be included in Cohort 2. The primary analysis for the remaining 4 treatment groups will combine data from both cohorts, while the accrued data from discontinued treatment groups will be analysed descriptively.

The analysis model will include UACR baseline value, treatment, and visit as fixed effect, and the stratifying factors (T2DM [yes/no] and eGFR [≥ 20 to < 30 mL/min/1.73 m²; or ≥ 30 to < 45 mL/min/1.73 m²; or ≥ 45 mL/min/1.73 m²]) as well as the Cohort variable (1 or 2) as covariates. Moreover, treatment-by-visit interaction will also be included in the model. The final analytical approach will be described in detail in the SAP. For the primary analysis, the main treatment comparisons to be evaluated are (in a fixed-sequence testing):

- 1 Overall comparison of the percentage changes from baseline in UACR at week 12 across all 4 treatment groups
- 2 Each of the 3 doses of AZD9977 in combination with dapagliflozin 10 mg versus dapagliflozin 10 mg in the following order:
 - 1. AZD9977 150 mg + dapagliflozin 10 mg versus dapagliflozin 10 mg
 - 2. AZD9977 50 mg + dapagliflozin 10 mg versus dapagliflozin 10 mg
 - 3. AZD9977 15 mg + dapagliflozin 10 mg versus dapagliflozin 10 mg

9.4.2.2 Secondary Endpoint

The dose-response relationship of percent change from baseline in UACR at 12 weeks will be assessed using data from dapagliflozin (10 mg) alone and 3 doses of AZD9977 (15, 50, or 150 mg) combined with dapagliflozin (10 mg).

More details of all these models will be provided in the SAP.

9.4.3 Pharmacokinetics

Plasma concentrations of AZD9977 and dapagliflozin will be listed and summarised by treatment groups, based on the PK Analysis Set.

9.4.4 Pharmacodynamics and Biomarkers

The following exploratory pharmacodynamic and biomarker endpoints will be summarised by treatment group based on the FAS:

- Change from baseline in serum NT-proBNP over time
- Change from baseline in blood uric acid, BUN, FPG, haematocrit, renin, ACTH, cortisol and copeptin levels over time
- Change from baseline in blood MCV, MCHC, RBC distribution width, erythrocyte count over time
- Change from baseline in urine Na⁺, K⁺, uric acid, urea, osmolality, glucose, creatinine, and cortisol levels over time
- Change from baseline in blood and urine biomarkers over time

The following analyses will not be part of the CSR:

- Dose/exposure of AZD9977 and dapagliflozin relative to safety and pharmacodynamic variables (eg, serum/plasma K⁺, eGFR, aldosterone)
- Exploratory research into genes/genetic variation that may influence response to treatment

Analysis for these exploratory objectives will be described in a separate analysis plan and results will be presented separately from the main CSR.

9.4.5 Safety

Safety analyses will be performed using the SS. Safety data will be presented using descriptive statistics unless otherwise specified.

In general, the baseline value for statistical analysis is the last non-missing value prior to administration of the first dose of IMP. Details are described in the SAP.

9.4.5.1 Adverse Events

Adverse events will be coded using the most recent version of the MedDRA that will have been released for execution at AstraZeneca or designee.

AEs will be presented for each treatment group by SOC and/or PT covering number and percentage of patients reporting at least 1 event and number of events where appropriate.

Only AEs occurring with an onset date, or worsening, on or after first dose of IMP and within 28 days after last dose of IMP will be presented in summary tables. Serious AEs occurring prior to start of IMP will be included in data listings.

An overview of AEs will present for each treatment group the number and percentage of patients with any AE, AEs with outcome of death, SAEs, and AEs leading to discontinuation of IMP, as well as AEs leading to IMP dose interruptions, and AEs leading to withdrawal from study as well as the number of individual occurrences in those categories.

Separate AE tables will be provided taken into consideration relationship as assessed by the investigator, maximum intensity, seriousness, death, and AEs leading to discontinuation of IMP as well as other action taken related to IMP, other significant AEs, and timing of events.

An additional table will present number and percentage of patients with most common AEs. Most common (eg, frequency of > 5%) will be defined in the SAP.

In accordance with the requirements of the FDA, a separate table will present non-serious AEs occurring in more than 5% of patients in any treatment group.

Key patient information will be presented for patients with AEs with outcome of death, SAEs, and AEs leading to discontinuation of IMP.

An AE listing for the SS will cover details for each individual AE; an AE listing for patients who were not exposed to IMP is presented separately.

Full details of AE analyses will be provided in the SAP.

9.4.5.2 Vital Signs

Vital sign parameters will be presented for each treatment group. Summary statistics for continuous variables cover n, mean, SD, minimum, Q1, median, Q3, and maximum.

For each scheduled post-baseline visit, descriptive statistics for all vital sign parameters will be presented for observed values and change from baseline.

Key patient information will be presented for patients with treatment-emergent changes in vital sign parameters outside of predefined criteria (see Section 9.4.5.6).

Supportive vital sign listings cover observed values and changes from baseline as well as abnormalities.

Details of vital sign analyses including definition of abnormality criteria (eg, definition of low, normal, high; clinically significant) and project-specific predefined criteria for treatmentemergent changes in relevant vital sign parameters (eg, systolic and diastolic BP) will be provided in the SAP.

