#### **Hypotension**

Symptomatic hypotension/decreased blood pressure will be evaluated by the analysis of BP measurements and the analysis of pre-defined AE preferred terms related to hypotension, as well as discontinuations due to hypotension. Hypotension will be presented as Number (%) of patients with:

- SBP<90 mmHg
- DBP <60 mmHg
- SBP<90 mmHg or DBP <60 mmHg\*
- SBP<90 mmHg and DBP <60 mmHg\*

- SBP<90 mmHg and decrease from baseline of >10mmHg\*
- DBP<60 mmHg and decrease from baseline of >10mmHg\*

All the BP outliers will be presented based on the on-treatment definition.

\* Recorded within the same measurement (or at a maximum within the same hour).

An overall summary table of frequencies of AE, SAEs, DAEs, and a summary table by PT will be provided based on a pre-defined list of preferred terms included in the Appendix C: List of preferred terms. The summary will be provided for all the AE with an onset date, or worsening, on or after first dose of investigational medical product (IMP) and within 28 days after last dose of IMP and for the on-treatment definition included in section 4.11.2 overall and by eGFR categories.

The number and percentage of cases will be tabulated by each treatment group.

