For haematology and chemistry, a shift table will present the baseline assessment against the minimum and the maximum on-treatment category.

Elevation in liver parameters for assessment of Hy's law will be done and reported appropriately if potential cases have been identified during the study.

Key patient information will be presented for patients with treatment-emergent changes in laboratory parameters outside of predefined criteria.

The following summaries will be also provided:

- Baseline versus maximum value on-treatment in each urinalysis laboratory parameter by treatment group (shift table)
- Maximum on-treatment ALT and AST by maximum total bilirubin for assessing Hy's Law criteria
- Treatment emergent haematology abnormalities and chemistry abnormalities by predefined criteria
- A summary of individual participant data for participants with Potential Hy's Law

By-participant listings of all laboratory data for the SS will be provided including participant identifier, treatment, age, sex, race, visit, category for lab test, lab test or examination name, result, standard units, reference range indicator. All values outside the clinical reference ranges will be flagged in the data listings. The abnormal values will be flagged with 'L' for values below the lower limit of the clinical reference range and 'H' for values above the upper limit of the clinical reference range and included in the listings.

The on-treatment definition is described in section 4.11.2.

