# 4.11.6 Vital Signs

Vital sign parameters will be presented for each treatment group based on SS.

Blood pressure and pulse rate will be assessed at the study site, as outlined in the SoA (Appendix A: Schedule of Activities), prior to blood collection for laboratory tests with the patient resting in a supine position using a completely automated device. Manual techniques will be used only if an automated device is not available.

Blood pressure and pulse measurements should be preceded by at least 5 minutes of rest for the patient in a quiet setting without distractions (e.g., television, cell phones) and will consist of 1 pulse and 3 BP measurements (3 consecutive BP readings will be recorded at intervals of at least 1 minute). The average of the 3 BP readings will be recorded on the eCRF.

Notable changes from pre-dose at each post-dose time point for vital sign parameters will be identified. The predefined criteria for notable changes in vital signs values are displayed in Table 7

Table 5 PCS vital signs predefined criteria

Vital sign	Level	Observed value	Notable change from baseline
Systolic BP (mmHg)	High	≥ 140	Increase of $\geq 20$
	Low	< 90	Decrease of $\geq 20$
Diastolic BP (mmHg)	High	≥ 90	Increase of $\geq 10$
	Low	< 60	Decrease of $\geq 10$
Pulse Rate (bpm)	High Low	≥ 100 < 50	Increase of $\geq 20$ Decrease of $\geq 20$

BP = Blood pressure.

The following summaries will be presented:

- A summary of the observed values and change from baseline in each vital sign parameter by treatment group and time point.
- A summary of key participant information for participants reporting notable changes outside predefined criteria in each vital sign parameter
- A summary of the number and percentage of participants experiencing notable changes from baseline outside predefined criteria, by vital sign parameter and treatment group.

By-participant listings of vital signs results, and findings will be provided.

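### SAP 4.11.6 sets no on-treatment limit for notable vital-sign changes, so the Visit 11 reading, taken after AZD9977 has stopped, is pooled with on-treatment readings (minor)

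*Protocol*

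**What the plan says.** **Protocol.** Section 9.4.5.2 plans one participant-level outlier output, with a cross-reference to 9.4.5.6: "Key patient information will be presented for patients with treatment-emergent changes in vital sign parameters outside of predefined criteria". It leaves the thresholds to the SAP: "project-specific predefined criteria for treatmentemergent changes in relevant vital sign parameters (eg, systolic and diastolic BP) will be provided in the SAP". Neither document defines treatment-emergent for a vital-sign reading.

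**SAP 4.11.6.** The rule is: "Notable changes from pre-dose at each post-dose time point for vital sign parameters will be identified". Table 5 gives thresholds for systolic BP, diastolic BP and pulse rate, in both directions. Two outputs follow:
- "A summary of the number and percentage of participants experiencing notable changes from baseline outside predefined criteria, by vital sign parameter and treatment group"
- "A summary of key participant information for participants reporting notable changes outside predefined criteria in each vital sign parameter"

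The section states no end to the window and uses neither treatment-emergent nor on-treatment.

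**Elsewhere in the SAP.** Under Hypotension in 4.11.3: "All the BP outliers will be presented based on the on-treatment definition". In 4.11.4, the Table 3 laboratory outliers count on-treatment values, and the section adds: "The on-treatment definition is described in section 4.11.2". That definition runs from first dose to 5 days after last dose.

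**Schedule.** The Schedule of Activities (protocol 1.3, SAP Appendix A) places vital signs at Visit 3 pre-dose, Visits 4 to 10, and Visit 11. Under protocol 6.7, study drug stops at the end-of-treatment visit and open-label dapagliflozin continues to Visit 11. For early discontinuers that continuation is at the investigator's judgement (7.1).

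**The concern.** The safety objective compares AZD9977 plus dapagliflozin with dapagliflozin alone. At Visit 11 nobody is taking AZD9977, so that reading says little about the contrast. The count table is not split by visit, so a participant whose only notable change occurred at Visit 11 cannot be told apart from one whose change occurred on drug. If the effect has worn off by then, the extra reading pulls the AZD9977 arms towards control, for rises and falls alike.

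There is also a consistency problem. SBP <90 and DBP <60 mmHg appear both in the 4.11.3 hypotension rows and in Table 5. One section is windowed and the other is not, so one report could carry two counts for the same threshold.

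**Working it through.** **1. Where Visit 11 falls.** Inputs from the Schedule of Activities: Visit 10 on Day 85 ±3, Visit 11 on Day 113 ±4, last dose one day before the end-of-treatment visit. For a completer:

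- Nominal: last dose Day 85 − 1 = 84, and 113 − 84 = 29 days. This agrees with the 4-week follow-up after last dose in protocol 4.1 to within a day.
- Range: last dose Day 81 to 87, Visit 11 Day 109 to 117. Shortest gap 109 − 87 = 22 days; longest 117 − 81 = 36 days.

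Visit 11 of a completer is thus always outside the last dose + 5 days window. Against the 28-day AE window it is nominally one day outside, but can fall on either side.

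**2. What feeds each output.**

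| Output | Window stated | Visit 11 of a completer |
|---|---|---|
| 4.11.3 low-BP rows | on-treatment | excluded |
| 4.11.4 laboratory outliers (Table 3) | on-treatment | excluded |
| 4.11.6 count by parameter and arm (Table 5) | none | included |
| 4.11.6 key-participant summary | none | included |

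The two 4.11.6 outputs draw on 8 post-dose visits (4 to 11), one of them off AZD9977. With the on-treatment window they would draw on 7.

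**3. Size from the extra visit alone (assumed rates).** The documents give no outlier rates. Take a per-visit probability p, independent across visits. The share with any notable change is 1 − (1 − p)^7 for 7 visits and 1 − (1 − p)^8 for 8. The last column is 125 times the difference.

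| p | 7 visits | 8 visits | Extra participants per arm of 125 |
|---|---|---|---|
| 1% | 6.8% | 7.7% | 1.2 |
| 2% | 13.2% | 14.9% | 2.2 |
| 5% | 30.2% | 33.7% | 4.4 |
| 10% | 52.2% | 57.0% | 6.0 |
| 20% | 79.0% | 83.2% | 5.2 |

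**4. Size of the between-arm dilution (assumed inputs).** Assume SBP change from baseline has SD 14 mmHg and correlation 0.5 between visits, with an AZD9977 effect of −5 mmHg at the 7 on-drug visits and 0 at Visit 11. Compare the share with any change of at least 20 mmHg with and without Visit 11.

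- Falls: about 55 to 56 of 125 in an AZD9977 arm, and about 35 to 38 in control. The difference goes from about 15.7 to 14.6 percentage points by simulation (15.8 to 14.8 by numerical integration of the same model). The ratio goes from 1.56 to 1.49.
- Rises: 15.9% to 19.3% in an AZD9977 arm, 28.3% to 30.2% in control. The ratio goes from 0.56 to 0.64.
- With SD 10 the ratio for rises goes from 0.32 to about 0.43.

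Both directions move towards control.

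**The case against.** Much of the case on the other side stands.

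- **Scope of the protocol's wording.** Treatment-emergent in 9.4.5.2 qualifies the key-patient output and the criteria left to the SAP. The protocol promises no vital-sign frequency table, though 9.4.5.3 does promise one for laboratory data. A reader might infer that the count table breaks the protocol. It does not; it is a SAP addition, and its problem is inconsistency within the SAP.
- **The term is undefined.** The last dose + 5 days rule is written for adverse events. Under a 28-day window, some Visit 11 readings would qualify as treatment-emergent. The 5-day window is preferable because the SAP already reuses it for blood pressure and laboratory values, not because the protocol requires it.
- **No mislabelling.** A reader might infer that the SAP counts Visit 11 changes as on treatment. It never says so; it calls them notable changes from baseline after dosing, which is literally true. The fault is that they are not separated.
- **Hypotension is protected.** A reader might infer that this named safety topic is exposed. Its rows in 4.11.3, which is the SAP counterpart of the protocol's cross-reference to 9.4.5.6, are on-treatment. That sentence sits under Hypotension after low-BP rows only, so it does not clearly reach Table 5 and does not cover BP rises or pulse rate.
- **ECG is a poor comparator.** Section 4.11.5 cites the on-treatment definition too, but no ECG is scheduled at Visit 11 and its outlier count is by visit.
- **Visit 11 stays visible** in the by-time-point statistics and listings. These do not undo the pooling in the count, but they limit the harm. The table shells, which are not available here, may also settle the window.

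**Conclusion.** The point holds as a minor one. As written, 4.11.6 pools one off-AZD9977 reading with seven on-treatment readings in the Table 5 count and in the key-participant summary. The latter also lacks the protocol's treatment-emergent qualifier. The affected content is BP rises, notable BP falls and pulse rate, plus a possible second count for SBP <90 and DBP <60 mmHg. SAP 4.14 declares no change to the planned analysis, so this looks like an omission.

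The timing of 22 to 36 days follows from the documents for completers. The size does not: it rests on assumed rates, variability, correlation and drug effect, and on no residual effect at Visit 11. On those assumptions the extra visit adds roughly 1 to 6 participants per arm, and the arm difference for systolic falls shrinks by about one percentage point. The primary analysis, type I error and sample size are untouched.

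**What to change.** Add to SAP 4.11.6 that the notable-change count and the key-participant summary use readings from first dose to last dose + 5 days, as in 4.11.2, applied to the date and time of the reading. Show Visit 11 changes in a separate off-AZD9977 column of both tables. Leave the by-visit descriptive statistics and the listings unchanged. With the same window in both places, the 4.11.3 and Table 5 counts for SBP <90 and DBP <60 mmHg can be reconciled.

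The cost is one SAP sentence, a window flag in the vital-sign programs and a matching edit to the table shells. No new data are needed and no safety information is lost.

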9.4.5.3 Laboratory

Laboratory parameters will be presented for each treatment group. Summary statistics for

continuous variables cover n, mean, SD, minimum, Q1, median, Q3, and maximum. Frequency tables cover number and percentage of patients in the respective category.

For each scheduled post-baseline visit, descriptive statistics for all clinical chemistry and haematology parameters will be presented for observed values and change from baseline.

A frequency table will present number of patients reporting at least one treatment-emergent change in laboratory parameters outside predefined criteria (see Section 9.4.5.6).

Elevation in liver parameters for assessment of Hy's law will be done and reported appropriately if potential cases have been identified during the course of the study.

Key patient information will be presented for patients with treatment-emergent changes in laboratory parameters outside of predefined criteria.

For urinalysis, a frequency table will present number of patients reporting at least 1 treatment-emergent increase in baseline category and/or a shift table will present the baseline assessment against the maximum on-treatment category.

Supportive laboratory listings cover observed values and changes from baseline for each individual patient as well as abnormalities.

Details of laboratory analyses including definition of abnormality criteria (eg, definition of low, normal, high; clinically significant) and project-specific predefined criteria for treatment-emergent changes in relevant laboratory parameters will be provided in the SAP.

